7.2 Duplicate Data

For unplanned duplicate data within a protocol-specified visit, the last measured value will be used for the analysis. If it is not possible to identify the “last measured value” the average of the duplicate values will be used.

No data will be excluded. All collected data will be listed.

7.3 Handling of Missing Data

7.3.1 Handling of Missing Data for Efficacy Evaluations

There is no imputation of missing data planned for efficacy evaluations.

7.3.2 Handling of Missing Data for Safety Evaluations

Adverse Event (AE) Summaries

With respect to summaries of AEs, only AEs that were treatment emergent will be tabulated. Treatment-emergent is defined as AEs with start date \geq date of first treatment administration.

- 1) If AE start date is completely missing, the date of first treatment administration will be taken as the start date of the event.
- 2) If AE start date is partially missing:

- a. If the day part of the start date is missing, the start date will be estimated to be equal to the date of first treatment administration, provided the start month and year are the same as the date of first treatment administration and the stop date either after the date of first treatment administration or completely missing. Otherwise, the AE will be assumed to have started on the first day of the month (01/MMM/YYYY)
- b. If the month part of the start date is missing, the start month will be estimated to be equal to the month of the date of first treatment administration or the following month after the month of the date of first treatment administration depending on the day part of the start date provided that the start year is the same as the year of date of first treatment administration and the stop date is either after date of first treatment administration or completely missing. Otherwise, the AE will be assumed to have started on the first month of the year (DD/Jan/YYYY)
- c. If both the day and month parts of the start date are missing, the start date will be estimated to be equal to the date of first treatment administration, provided the start year is the same as year of date of first treatment administration and the stop date is either after the date of first treatment administration or completely missing. Otherwise, the AE will be assumed to have started on first day and first month of the year (01/Jan/YYYY)
- d. If all day, month and year parts of the start date are missing, the start date will be estimated to be equal to the date of first treatment administration (and thus treatment emergent) provided that the stop date is either after the date of first treatment administration or completely missing. Otherwise, the start date will be estimated to be the first day of the same year as the stop date.

3) If AE stop date is partially or completely missing:

- a. If only the day portion of the stop date is unknown, the day will be assumed to be last date of the month (e.g., ??-Jan-2004 will be treated as 31-Jan-2004).
- b. If both the day and month of stop date are unknown, the event will be assumed to have ceased on the last day of the year (e.g., ??-??-2004 will be treated as 31-Dec-2004).

c. If the stop date is completely missing, the event will be assumed to be “Ongoing”.

Concomitant medications (CM) Summaries

- 1) If CM start date is completely missing then the date of first treatment administration will be taken as the start date of the medication
- 2) If CM start date is partially missing:
 - a. If the Day part of the start date is missing, the CM will be assumed to have started on the first day of the month (01/MMM/ YYYY)
 - b. If the month part of the start date is missing, the CM will be assumed to have started on the first month of the year (dd/Jan/ YYYY)
 - c. If both the day and month parts of the start date are missing, the CM will be assumed to have started on first day and first month of the year (01/Jan/ YYYY)

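### SAP 7.3.2 has two conflicting rules for an AE with no start date, and its strict stop-date test makes an event that resolves on Day 0 non-emergent

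*SAP*

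**What the plan says.** SAP 7.3.2 defines an AE as treatment-emergent if its start date is the first-dose date or later, and states that "only AEs that were treatment emergent will be tabulated". SAP 8.3.1 gives the same inclusive definition.

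For a start date that is wholly missing there are two rules:

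- Rule 1: "If AE start date is completely missing, the date of first treatment administration will be taken as the start date of the event". No condition is attached.
- Rule 2d, listed under partially missing dates but describing a start with day, month and year all absent. It assigns the first-dose date "and thus treatment emergent) provided that the stop date is either after the date of first treatment administration or completely missing". If that condition fails: "Otherwise, the start date will be estimated to be the first day of the same year as the stop date".

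Rules 2a, 2b and 2c (day, month, or both missing) use the same stop-date test. Their fallbacks are the first of the month, January, and 1 January respectively.

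For medications, a wholly missing start also goes to first dose: "If CM start date is completely missing then the date of first treatment administration will be taken as the start date of the medication". Partial dates go to the earliest possible date with no comparison to first dose. With the day missing, "the CM will be assumed to have started on the first day of the month". With the month missing, "the CM will be assumed to have started on the first month of the year". With both missing, "the CM will be assumed to have started on first day and first month of the year".

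**The concern.** Rules 1 and 2d apply to the same record and cannot both be programmed. Where they differ, one puts the event in the TEAE tables and the other removes it, so a programmer would have to choose without guidance.

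The second defect would remain even if only one rule were kept. The inclusive definition counts an event that begins on the day of first dose. The imputation rules, however, let an incomplete start date take the first-dose date only if the event ended on a later day. A short reaction that begins and ends on Day 0 therefore fails the test and is moved to before treatment.

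Safety and tolerability is the primary objective (SAP 2.1), and Protocol 1.4 describes the study as first-in-human. Protocol 4.1.2 schedules an AE evaluation after the first dose on Day 0, so this is a kind of event the study sets out to capture.

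**Working it through.** The plan states no figure for this point. The check applies the rules as written.

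**Step 1: rules 1 and 2d side by side.** Illustrative first dose 15 March 2018, AE start wholly missing.

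| Stop date | Rule 1 | Rule 2d | Agree? |
|---|---|---|---|
| Missing | 15 March, emergent | 15 March, emergent | Yes |
| 25 March (Day 10) | 15 March, emergent | 15 March, emergent | Yes |
| 15 March (Day 0) | 15 March, emergent | 1 January, not emergent | No |
| 14 March (Day -1) | 15 March, emergent, start later than stop | 1 January, not emergent | No |

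**Step 2: which rows can occur.** Protocol 10.2 opens AE reporting at the first randomized treatment, and Protocol 8.4 sends earlier events to medical history. The last row should therefore not reach the AE dataset. The Day 0 row can.

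**Step 3: how often a Day 0 event is made non-emergent, given that such a record exists.** Take each date in a 365-day year as the first-dose date, with the event starting and stopping on that date.

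- Rule 2a (day missing): the fallback is the first of the month. This precedes first dose unless dosing was on the 1st: 365 - 12 = 353 of 365.
- Rule 2b (month missing): the fallback is the same day in January. This precedes first dose unless dosing was in January: 365 - 31 = 334 of 365.
- Rules 2c and 2d: the fallback is 1 January: 365 - 1 = 364 of 365. This 364 is also the number of first-dose dates on which rules 1 and 2d conflict for a Day 0 stop.

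**Step 4: medication dates.** Assume first-dose dates spread evenly over a 365-day year and true starts spread evenly over Days 1 to 84 (treatment) or Days 1 to 112 (to the follow-up visit). With only the day missing, the imputed date falls before first dose only if the drug began in the first-dose month and dosing was not on the 1st.

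- Pairs of first-dose date and later start date in the same month: seven 31-day months, four 30-day months and one 28-day month give 7 x 465 + 4 x 435 + 378 = 5,373.
- Less pairs with first dose on the 1st: 7 x 30 + 4 x 29 + 27 = 353, leaving 5,020.
- Days 1 to 84: 5,020 / (365 x 84) = 5,020 / 30,660 = 16.4%.
- Days 1 to 112: 5,020 / (365 x 112) = 5,020 / 40,880 = 12.3%.

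Under the same assumptions the share is 80-84% when the month is missing and 84-88% when day and month are missing. A medication with no start date is always placed on Day 0, however long it has been taken.

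**The case against.** The strongest reply on the AE rules is that the two agree whenever the stop date is missing or later than first dose, which covers ongoing events and almost all others. The remaining case needs a stop date of Day 0 alongside a start date not fully known, although the event was assessed at the same visit. That should be rare and could often be settled by a query. All of this stands, and it limits the size of the point.

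One could also read 2d as simply the detail behind rule 1. The text does not say so, and that reading leaves the Day 0 defect in place, because rule 1 is the rule that classifies a Day 0 event correctly.

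A reader might infer more from the medication rules: that a newly started Parkinson's drug could look pre-existing, or background amantadine newly initiated, and so change who is in the per-protocol set used for the primary efficacy analysis. It is true that Protocol 7.1 prohibits initiation and that SAP 8.1.2 lists excluded medication as a deviation category. The documents do not support the further step:

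- The medication rules sit under a heading for summaries.
- The SAP has no variable for drugs initiated on study.
- Per-protocol membership turns on major violations identified before lock (SAP 6.2), and deviations are documented in the CRFs (Protocol 13.4).
- Drugs are listed at screening and TV0, and subjects are asked about new ones at each visit (Protocol 4.1.1, 4.1.2 and 7).
- SAP 8.1.4 summarizes prior and concomitant medications by treatment group with no date cut-off. Protocol 9.9.3 also mentions stage of the study, but the SAP does not carry that over.

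**Conclusion.** The AE part holds. Rules 1 and 2d conflict when a known stop date is on or before first dose. The strict stop-date test in 2a to 2d also contradicts the SAP's inclusive definition for an event that resolves on Day 0. Given such a record, the event is wrongly made non-emergent for 334 to 364 of 365 first-dose dates, depending on which date parts are missing. The number of such records cannot be worked out from the documents and is probably small. It would be too strong to say that treatment-emergent status is unreliable for every AE without a start date, because the rules agree in all other cases.

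The medication part is minor. The rules can date an on-study start before first dose (about 12-16% of starts with only the day missing, under evenly spread dates). That is a share of an unknown and possibly zero number of records. No planned SAP output and no per-protocol decision is shown to depend on it.

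**What to change.** In SAP 7.3.2:

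1. Delete AE rule 1 and keep 2d as the only rule for a wholly missing start date, placed under its own heading rather than among partial dates.
2. In 2a to 2d, replace *after* with *on or after* the first-dose date in the stop-date condition.

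Make both changes together. Deleting rule 1 alone would leave the Day 0 event non-emergent under 2d.

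As an optional safeguard, add one sentence saying that review of prohibited-medication deviations uses source and visit records, not imputed medication dates.

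The cost is a few words in the SAP and a small programming specification change before database lock. No new data are needed.

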7.4 Multiplicity

No Multiplicity adjustment will be implemented for this Phase 2 clinical trial.

7.5 Covariates

Baseline values will be used as covariates for efficacy analysis.

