### 3.1.2 INCLUSION CRITERIA

Subjects will be eligible for enrollment in the study only if they meet ALL of the following criteria:

1. Male or female subjects who are between 30 and 79 years old inclusive with a clinical diagnosis of Parkinson's disease as per UK Brain Bank Criteria for two (2) years or less at screening.
2. Hoehn and Yahr I or II at screening.
3. Subjects who are newly diagnosed & currently not on any Parkinson's disease medication (or) subjects who are on stable doses for at least 4 weeks prior to screening on Amantadine or anticholinergics for treatment of Parkinson's disease.
  1. Note: Subjects that had anti-parkinsonian medication (including levodopa, dopamine agonists, entacapone and monoamine oxidase-B inhibitors) discontinued at least 60 days prior to screening, e.g., for intolerance, may be considered eligible if all other eligibility requirements are met.
4. Women of child-bearing potential should use reliable contraception. Acceptable methods of contraception include: surgical sterilization (e.g. bilateral tubal ligation), hormonal contraception (implantable, patch, and oral), and double-barrier methods (condom, diaphragm and spermicide are each considered a barrier). Women of child-bearing potential are defined as women physiologically capable of becoming pregnant, UNLESS they meet the following criteria:
  1. Post-menopausal: 12 months of natural (spontaneous) amenorrhea or 6 months of spontaneous amenorrhea with serum Follicle Stimulating Hormone (FSH) levels  $> 40\text{mIU}/\text{m}$ , OR;
  2. 6 weeks post surgical bilateral oophorectomy with or without hysterectomy
5. If a male and heterosexually active with a female of childbearing potential, the subject must agree to use a double barrier method of birth control (or must have been surgically sterilized) and to not donate sperm during the study.
6. Without clinically significant abnormalities in physical exam, neurological exam and laboratory assessments (urine/blood routine, biochemical tests and ECG) which would exclude the subject from the study in the opinion of the Investigator. For Aspartate aminotransferase (AST), alanine aminotransferase (ALT) and alkaline phosphatase (ALP) the screening levels should be  $\leq 2$  times upper limit normal.
7. Subject is capable of providing informed consent and is willing to sign the ICF prior to study Screening and agrees to comply with the study protocol requirements.

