### 7.1 PROHIBITED MEDICATION

The following treatments and medications are prohibited throughout the study

1. Initiation of any anti-parkinsonian medication (including levodopa, dopamine agonists, entacapone and monoamine oxidase-B inhibitors) for the duration of the trial.
2. Initiation of Amantadine or anticholinergics for newly diagnosed subjects or change in the dosage of Amantadine or anticholinergics during the trial for subjects who were on stable doses for 4 weeks prior to screening.

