### Part III: Motor Examination

Overview: This portion of the scale assesses the motor signs of PD. In administering Part III of the MDS-UPDRS the examiner should comply with the following guidelines:

At the top of the form, mark whether the patient is on medication for treating the symptoms of Parkinson's disease and, if on levodopa, the time since the last dose.

Also, if the patient is receiving medication for treating the symptoms of Parkinson's Disease, mark the patient's clinical state using the following definitions:

**ON** is the typical functional state when patients are receiving medication and have a good response.

**OFF** is the typical functional state when patients have a poor response in spite of taking medications.

The investigator should "rate what you see". Admittedly, concurrent medical problems such as stroke, paralysis, arthritis, contracture, and orthopedic problems such as hip or knee replacement and scoliosis may interfere with individual items in the motor examination. In situations where it is absolutely impossible to test (e.g., amputations, plegia, limb in a cast), use the notation "**UR**" for Unable to Rate. Otherwise, rate the performance of each task as the patient performs in the context of co-morbidities.

All items must have an integer rating (no half points, no missing ratings).

Specific instructions are provided for the testing of each item. These should be followed in all instances. The investigator demonstrates while describing tasks the patient is to perform and rates function immediately thereafter. For Global Spontaneous Movement and Rest Tremor items (3.14 and 3.17), these items have been placed purposefully at the end of the scale because clinical information pertinent to the score will be obtained throughout the entire examination.

At the end of the rating, indicate if dyskinesia (chorea or dystonia) was present at the time of the examination, and if so, whether these movements interfered with the motor examination.

**3a** Is the patient on medication for treating the symptoms of Parkinson's Disease?  No  Yes

**3b** If the patient is receiving medication for treating the symptoms of Parkinson's Disease, mark the patient's clinical state using the following definitions:

**ON**: On is the typical functional state when patients are receiving medication and have a good response.

**OFF**: Off is the typical functional state when patients have a poor response in spite of taking medications.

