2.3.2 Method of Treatment Assignment, Randomization Ratio, and Stratification

The randomization in this multi-center study will be applied centrally across the sites and will use a mixed block size of 3 and 6 with a 1:1:1 ratio of DA-9805 (45mg/day), DA-9805 (90mg/day) and Placebo Treatment groups.

Subjects who have provided written informed consent and have met all the inclusion criteria and none of the exclusion criteria will be randomized to one of the treatment groups mentioned in [Table 2-1](#) based on a randomization schedule. An individual, independent of the clinical trial team, will develop the randomization schedules.

The actual randomization assignment will be made through an Interactive Web Based System (IWRS) called WebView (Amarex Clinical Research, Germantown MD). WebView is a Secure Socket Layer (SSL) web portal that allows 24/7 access to clinical trial information. Authorization is based on approved access control list (ACL) that determines a user's access to the site. The Amarex Technology department, who is not otherwise involved with the study, is responsible for the implementation and maintenance of WebView. Each user will be trained in how to use the website. A WebView user manual will be supplied to all study personnel with instructions on using the website.

The Randomization/Supply module of WebView allows authorized users to request randomization (Site Personnel only) into the trial. The detailed description and instructions are included in the

WebView user manual. Amarex Clinical Research has further documentation and validation of WebView specifically with regards to preserving the blinding of this study.

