7.6 Stratification Factors

There are no stratification factors for this study.

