8.2.1 Primary Efficacy Outcome

The primary efficacy outcome for this study is change in motor MDS-Unified Parkinson Disease Rating Scale (MDS-UPDRS) total score from baseline at week 12.

Change in motor MDS-UPDRS total score from baseline at week 12 will be calculated for each subject using the formula in [Section 7.9.5](#). Both Treatment Group 1 and 2 will be compared with Group 3 using Analysis of Covariance (ANCOVA) with baseline value as a covariate to compare the change in motor MDS-UPDRS total score from baseline at week 12. 95% confidence interval

around the difference and P value for the treatment effect will be reported.

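### Background amantadine or anticholinergic use varies at entry and is recorded at baseline, but it is neither a stratum nor a covariate; adding the TV0 status to the ANCOVA would be cheap protection against chance imbalance

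*SAP*

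**What the plan says.** Inclusion criterion 3 (Protocol 3.1.2) opens the trial to two background states. One is "Subjects who are newly diagnosed & currently not on any Parkinson's disease medication"; the other is "subjects who are on stable doses for at least 4 weeks prior to screening on Amantadine or anticholinergics for treatment of Parkinson's disease". A note to the criterion also allows subjects who stopped other antiparkinsonian drugs at least 60 days before screening. During the trial, Protocol 7.1 prohibits starting amantadine or anticholinergics, and also prohibits "change in the dosage of Amantadine or anticholinergics during the trial for subjects who were on stable doses for 4 weeks prior to screening".

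Allocation is central and "will use a mixed block size of 3 and 6 with a 1:1:1 ratio" (SAP 2.3.2). SAP 7.6 states: "There are no stratification factors for this study". The general covariate rule in SAP 7.5 is "Baseline values will be used as covariates for efficacy analysis". SAP 8.2.1 makes it specific for the primary outcome: "Analysis of Covariance (ANCOVA) with baseline value as a covariate". The secondary outcomes follow similar methods (SAP 8.2.2).

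Item 3a of MDS-UPDRS Part III (Protocol Appendix 1) asks: "Is the patient on medication for treating the symptoms of Parkinson's Disease". Protocol 4.1.2 places the MDS-UPDRS among the TV0 assessments done before randomization, so the answer is a true baseline value.

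**The concern.** The motor score is taken with no symptomatic drug in some subjects and on a stable symptomatic drug in others. If the two groups change differently over 12 weeks by an amount that the baseline score does not predict, an uneven split between a dose arm and placebo moves the estimated treatment difference. Blocks of 3 and 6 equalise arm sizes, not medication status, and with 20 per arm uneven splits are common.

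Two features of the plan add to this:

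- The primary analysis uses the PP population (SAP 8.2), and receipt of an excluded medication is a listed deviation category (SAP 8.1.2). The prohibited acts differ by background group, so balance at randomization need not carry over to the analysed set.
- Nothing in the SAP commits to adjusting for background medication. If an imbalance appeared after unblinding, any adjustment would be post hoc.

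**Working it through.** **Inputs from the documents.** 60 subjects, 20 per arm, 1:1:1 (SAP 4 and 2.3.2); no strata; ANCOVA on the baseline score; two-sided 0.05. The sample size was chosen by clinical judgment, so there is no power figure to reproduce.

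**Inputs not in the documents (assumed, with ranges).** *p* is the share of subjects on amantadine or anticholinergics. *g* is the effect of medication status on 12-week change given the baseline score, in residual SDs.

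**Step 1: chance of imbalance.** Let *f* be the Binomial(20, *p*) probability. For a difference of at least *k* subjects in at least one of the two dose–placebo comparisons,

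P = 1 − Σ_c f(c) · [Σ_{a: |a−c|<k} f(a)]²,

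where *c* is the placebo count. Two subjects of 20 are 10 points; four are 20 points.

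| Share of users *p* | ≥10 points, one comparison | ≥10 points, at least one | ≥20 points, one comparison | ≥20 points, at least one |
|---|---|---|---|---|
| 5% | 25% | 41% | 1% | 2% |
| 10% | 42% | 63% | 6% | 11% |
| 20% | 55% | 78% | 16% | 28% |
| 30% | 60% | 82% | 23% | 37% |
| 50% | 64% | 85% | 27% | 43% |

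Hand check: the SD of the difference in proportions is √(2p(1−p)/20). At *p* = 0.20 this is √0.016 = 0.126, so 10 points is less than one SD.

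Fixing the total number of users at 60*p* and splitting them at random over three arms of 20 (hypergeometric) gives 69% at *p* = 0.10 and 86% at *p* = 0.50 for 10 points. For 20 points it gives 11% and 43%. The two methods together span about 63% to 86% and 11% to 43%.

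**Step 2: size of the shift.** Shift ≈ *g* × imbalance.

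- *g* = 0.5: 0.5 × 0.20 = 0.10 SD.
- *g* = 1.0: 1.0 × 0.20 = 0.20 SD.
- In scale points, if the groups' mean changes differ by 2 to 5 points (assumed): 0.20 × 2 = 0.4 to 0.20 × 5 = 1.0 point.

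The standard error of a dose–placebo difference is about √(2/20) = 0.316 SD; simulation of the ANCOVA gives about 0.32. A shift of 0.10 SD is therefore 0.10/0.32 ≈ 0.31 of a standard error.

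**Step 3: what the covariate does.** Simulation of three arms of 20, 4,000 runs per setting, at *p* = 0.20. The shift is the mean among runs with an imbalance of at least 20 points, so it runs a little above Step 2.

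| *g* | Shift without → with covariate | SE without → with | Power at a 0.9 SD effect without → with |
|---|---|---|---|
| 0 | about 0 → about 0 | 0.318 → 0.321 | 79.2% → 78.5% |
| 0.5 | 0.11 → about 0 | 0.325 → 0.321 | 77.2% → 77.9% |
| 1.0 | 0.25 → about 0.02 | 0.342 → 0.320 | 73.0% → 79.0% |

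Averaged over all randomizations with no treatment effect, neither model is biased. Rejection rates at *p* from 0.10 to 0.30 and *g* from 0 to 1.0 ran from 4.4% to 6.2% without the covariate and from 4.3% to 6.0% with it.

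**Step 4: break-even for precision.** If status predicts nothing, the cost is 0.321/0.318 = 1.009, about 1% in SE or 1.9% in variance. Leaving it out inflates residual variance by *g*²p(1−p). Setting this equal to 0.019 gives *g* = √(0.019/0.09) = 0.46 at *p* = 0.10 and √(0.019/0.16) = 0.34 at *p* = 0.20. It is somewhat lower at larger shares: √(0.019/0.25) = 0.28 at *p* = 0.50.

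**Step 5: degrees of freedom.** With all 60 subjects in one model, 60 − 3 arms − 1 covariate = 56, and 55 after the addition. The PP set will have at most this.

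**The case against.** The strongest reply is that nothing is broken. ANCOVA on the baseline score is a valid analysis of a randomized comparison, and a further covariate is a matter of choice. That stands. A reader might infer that the mixed entry makes the planned analysis biased or inflates type I error; the documents do not support this, because medication status is a pre-randomization factor and the comparison is unbiased on average without it.

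A reader might also infer that a large imbalance is to be expected. No share of users is stated. Entry within two years of diagnosis at Hoehn and Yahr I or II is compatible with few users, and a 20-point imbalance is less likely than not at every share examined. Only the 10-point imbalance is more likely than not, at shares of 10% or more. Nor would a covariate remove an imbalance: the arm counts stay as they are, and the estimate is corrected only so far as status predicts change beyond baseline.

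Stable dosing also weighs against a large effect. A constant drug effect is present at both baseline and week 12, so the change score and the baseline covariate absorb much of it. This makes *g* uncertain and possibly small. It does not show that *g* is zero, since the groups could still change at different rates.

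Medication summaries by arm are already planned (SAP 8.1.4), so an imbalance would be visible. Seeing it after unblinding is not the same as having a pre-specified adjustment.

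Finally, a yes/no item pools never-treated subjects with those who stopped other drugs at least 60 days earlier. That is a limit of the covariate, not a reason against it.

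**Conclusion.** The point holds as a low-cost improvement, not as an error in the plan. Inclusion criterion 3 admits subjects with and without a stable symptomatic drug, randomization does not stratify on this, and the model ignores a status already recorded at TV0. The planned ANCOVA is valid on average; the benefit is protection of the estimate in the randomization that actually occurs.

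The size rests on two assumptions that the documents do not supply. With 10% to 50% users, at least one dose arm differs from placebo by 10 points or more with a chance of about 63% to 86%, and by 20 points or more with a chance of about 11% to 43%. With a 0.5 SD effect of status given baseline, a 20-point imbalance shifts the estimate by about 0.1 SD, roughly a third of its standard error. A material power gain appears only near a 1.0 SD effect, which nothing in the documents establishes. The primary objective is safety and tolerability, which further limits the weight of the point.

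**What to change.** In SAP 7.5 and 8.2.1, and by reference 8.2.2, pre-specify symptomatic PD medication status at TV0 (yes/no) as a second covariate in the efficacy ANCOVAs.

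- **Source:** item 3a, cross-checked against the medication record. Use the TV0 value only, because the item is asked again after randomization. The record should not stand alone: SAP 7.3.2 sets a completely missing medication start date to the first-dose date, which could make a background drug look as if it began on study.
- **Too few users:** drop the covariate at blinded review if the number of users is too small to estimate it. State the minimum number in the SAP beforehand and apply it to the pooled count.
- **Reporting:** add the status to the baseline table by arm (SAP 8.1.3).

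Cost: a sentence or two in the SAP, no new data, and one degree of freedom. The SE is about 1% larger if the status is not prognostic. There is no net precision gain unless its effect exceeds roughly 0.35 to 0.5 SD at 10% to 20% users, or a little less at higher shares.
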